### **8.7.2 Return and/or destruction of treatments**

Patients are to return all IMP (unused, in-use or used wallet[s]) at each on-site visit (see [Section 1.2](#)).

At Visit 4 (Week 1), because no IMP re-supply is planned during this visit, patients will be sent home after this visit with the in-use wallet(s) dispensed at randomization.

Patients are to return all the used, in-use and unused IMP at Visit 9 (or final assessment on-treatment visit in case of permanent premature discontinuation).

All used, partially-used or unused IMPs will be retrieved by the Sponsor or Delegate. A detailed site and patient treatment log of the returned IMP will be established with the Investigator (or the pharmacist) and countersigned by the Investigator and the monitoring team.

## **8.8 CONCOMITANT MEDICATION**

A concomitant medication is any treatment received by the patient concomitantly to any IMP(s). The IMP includes placebo, sotagliflozin 400 mg and sotagliflozin 200 mg.

All concomitant medications should be documented on the Medications page of the e-CRF. This includes all non-IMP treatments that are taken by the patients at any time during the clinical study, beginning at Visit 1.

Additionally, all medications taken in the 3 months prior to Visit 1 and prior use of SGLT2 inhibitors should be reported.

### **8.8.1 Prohibited prior and concomitant medications**

During the study treatment period, the following medications are prohibited:

- Initiation of any antidiabetic agents, including oral or injectable antihyperglycemic agents other than the IMP is not allowed before the rescue therapy
- Systemic use of glucocorticoids is not allowed for more than 10 consecutive days (topical, ophthalmic, nasal spray or inhaled applications are allowed)
- Initiation of any weight loss drugs (eg, phentermine, orlistat)
- Investigational medicinal products in any other clinical study
- SGLT2 inhibitors (eg, canagliflozin, dapagliflozin, or empagliflozin) are not allowed for rescue

Note: short term use (< 10 consecutive days) of the prohibited medication, eg, short-acting insulin for treatment of acute illness or surgery is allowed.

Reduction of digoxin dose should be considered because sotagliflozin acts as a weak P-gp inhibitor and increases systemic exposure to digoxin. Patients taking sotagliflozin with concomitant digoxin should have digoxin concentrations monitored and doses reduced as needed. In addition, other P-gp substrates may be affected and the labels of P-gp substrate drugs should be consulted with regards to monitoring and dose adjustments.

Other medications which are unlikely to interfere with the PK or PD of the IMP or confound interpretation of the study endpoints are allowed as needed and following discussion between the Investigator and the Sponsor. However, doses of chronically administered medicines should be kept fixed during the trial if at all possible.

After premature permanent discontinuation of the IMPs, any treatments (other than SGLT2 inhibitors) are permitted, as deemed necessary by the Investigator.

The dose of all antihypertensive agents should be kept constant during the 12 weeks following randomization and no antihypertensive agents should be added or withdrawn for the 12 weeks following randomization unless it is considered necessary for safety reasons.

### **8.8.2 Concomitant diabetes therapy**

Non-IMP treatment is defined as the rescue medication(s) that will be used to treat hyperglycemia when a patient's hyperglycemia reaches the rescue threshold. Except for SGLT2 inhibitors, any approved medication(s) including oral antidiabetic drugs or insulin can be prescribed at the Investigator's discretion to treat the hyperglycemia. The regimen of the rescue medications will be in accordance with local standard of care and prescribing practice.

## **8.9 POSTSTUDY TREATMENT**

Because sotagliflozin may reduce BP, adjustment of antihypertensive medication may be needed during the study in patients with hypertension. Conversely, monitoring for an increase in BP should be performed after withdrawal of study medication. If the BP is elevated after withdrawal of study treatment, the Investigator should consider adding or adjusting antihypertensive medication.

## 9 ASSESSMENT OF INVESTIGATIONAL MEDICINAL PRODUCT

### 9.1 EFFICACY ENDPOINTS

The methods of assessment of efficacy endpoints are detailed in [Section 9.1.4](#).

#### 9.1.1 Primary efficacy endpoint

- Comparison of sotagliflozin 400 mg versus placebo in change from Baseline to Week 26 in HbA1c (%).

#### 9.1.2 Secondary efficacy endpoints

The continuous secondary efficacy endpoints are:

- Comparison of sotagliflozin 400 mg versus placebo for:
  - Change from Baseline to Week 26 in 2-hour PPG following a MM
  - Change from Baseline to Week 26 in FPG
  - Change from Baseline to Week 26 in body weight
  - Change from Baseline to Week 12 in SBP for patients with baseline SBP  $\geq$ 130 mmHg
  - Change from Baseline to Week 12 in SBP for all patients
  - Proportion of patients with HbA1c <6.5%, <7.0% at Week 26
- Comparison of sotagliflozin 200 mg versus placebo for:
  - Change from Baseline to Week 26 in HbA1c
  - Change from Baseline to Week 26 in 2-hour PPG following an MM
  - Change from Baseline to Week 26 in body weight
  - Change from Baseline to Week 12 in SBP for all patients

#### 9.1.3 Other efficacy endpoints

Comparison of sotagliflozin 400 mg and 200 mg doses versus placebo for:

- Change from Baseline to Week 12 in SBP for patients with baseline SBP <130 mmHg
- Changes from Baseline to Week 12 in DBP
- Proportion of patients achieving SBP <130 mmHg for those with Baseline SBP  $\geq$ 130 mmHg
- Proportion of patients achieving DBP <80 mmHg for those with Baseline DBP  $\geq$ 80 mmHg

- Change from Baseline in:
  - Urine ACR, UGE, and urine GCR
  - Serum creatinine
  - eGFR
- Proportion of patients with reduction in body weight by  $\geq 2\%$ ,  $\geq 5\%$ , and  $\geq 10\%$  from Baseline
- Change from Baseline to Week 26 in SBP for all patients and for patients with Baseline SBP  $\geq 130$  mmHg
- Proportion of patients requiring rescue for hyperglycemia

Comparison of sotagliflozin 200 mg versus placebo for:

- Change from baseline in FPG at Week 26
- Change from baseline in SBP at Week 12 for patients with Baseline SBP  $\geq 130$  mmHg
- Proportion of patients with HbA1c  $< 6.5\%$ ,  $< 7.0\%$  at Week 26

#### **9.1.4 Assessment methods of efficacy endpoints**

##### **9.1.4.1 HbA1c**

Hemoglobin A1c will be assessed at Screening (Visit 1), Baseline (Visit 3), and all on-site visits during the double-blind treatment period with the exception of Week 1 (Visit 4).

For the eligibility and efficacy assessments of the study, HbA1c is measured by a certified level I “National Glycohemoglobin Standardization Program” central laboratory to allow estimation of the change from Baseline to Week 26 in HbA1c and the proportion of patients with HbA1c  $< 6.5\%$ ,  $< 7.0\%$  at Week 26.

If a patient needs to receive rescue antidiabetic medication, assessment of HbA1c should be performed before the introduction of the rescue medication.

##### **9.1.4.2 Postprandial glucose and mixed meal tolerance test**

Patients will undergo assessment of PPG at Visit 3 (Baseline) and Visit 9 (Week 26) via a mixed meal tolerance test (MMTT) to allow estimation of change from Baseline to Week 26 in 2-hour PPG following a MM. Full details of the MMTT procedure at Baseline and Week 26 are presented in [Appendix B](#).

At Visit 3 (Baseline) and Visit 9 (Week 26), PPG values will be assessed by MMTT at baseline (fasting) and 2 hours after consuming a standard mixed liquid breakfast meal.

The first dose of double-blind IMP on Day 1 (Baseline; Visit 3) will be given **after** completion of the 2-hour PPG collection. For the Week 26 standardized MM, the patient should take the dose of

double-blind IMP immediately **after** the fasting blood samples are obtained, and approximately 30 minutes **before** ingestion of the standardized MM begins.

Plasma concentration samples at Week 26 should be taken at the same times as the fasting blood sample and the 2-hour central laboratory plasma PPG collection (see [Section 9.3.1.1](#)).

The composition and the quantity of the standard mixed liquid breakfast meal must be identical throughout the study; see [Appendix B](#) for further details.

All patients should undergo the standardized MMTT at Visit 9 (Week 26), including those rescued before Visit 9.

In case of permanent discontinuation of the treatment with IMP before Visit 9 (Week 26), every effort will be made to have the patient return to the site at the time of their Visit 9 (Week 26); however the MMTT should not be performed at this or any other visit following a Premature EOT visit.

On the days of the MMTT, patients will come to the investigational site in the morning, in fasting conditions for at least 8 hours and must not eat any food or drink, except water, before the scheduled standardized meal test.

The exact times of the IMP administration, standard mixed liquid breakfast meal intake, and the blood draws are to be documented.

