#### **10.1.2.1.2 On-site Visit 9 at Week 26 – End-of-treatment**

The following will be performed at this visit:

- IRT to be notified for EOT (if EOT visit is also last visit, IRT should be notified for end of study)
- IMP accounting and compliance
- Patient diary, including hypoglycemia log, is collected/reviewed and dispensed and instructions/training are provided as needed
- Concomitant medications are assessed
- AEs/SAEs/AESI/EOSI and hypoglycemia (if any) are reported
- Patients are evaluated for glycemic rescue (see [Section 9.1.4.7](#))
- Measurement of body weight
- Complete physical examination including vital signs (SBP and DBP, temperature, heart rate, and respiratory rate). Three separate seated BP and heart rate measurements should be taken with at least 1 minute between measurements following a 5-minute rest period, and prior to phlebotomy (see [Appendix D](#) for details of BP procedure)
- Diet and exercise instruction is provided
- Instruction on DKA symptoms is provided
- Instruction on basic GU hygiene and hydration is provided (see [Appendix C](#))
- 12-lead ECG, prior to the IMP administration
- Fasting SMBG is assessed
- Standard MMTT (2-hour PPG measurements) (not to be performed if patient has discontinued prior to Premature EOT visit; see [Section 10.3.4](#))
- The following laboratory testing (by the central laboratory):
  - Fasting plasma glucose
  - HbA1c
  - Urine pregnancy testing for WOCBP (any positive urine test results must be confirmed by a serum pregnancy test)
  - Hematology
  - Clinical chemistry to include amylase and lipase
  - Fasting lipids
  - Urinalysis (dipstick and microscopy)
  - Urine analysis for albumin, calcium, glucose, and creatinine

- Additional laboratory testing at this visit:
  - Markers of intestinal transit and absorption (vitamins B6, B12, K, E, and A, serum folate, and ferritin)
  - Markers of bone and calcium metabolism (serum and urinary calcium, serum 25-hydroxyvitamin D, serum 1,25-dihydroxyvitamin D, serum and urinary phosphorus, serum PTH, markers of bone resorption [serum NTX, serum  $\beta$ -CTX-1], and bone formation [serum P1NP])
  - [REDACTED]
- Plasma concentration samples (pre-dose and 2 hours 30 minutes post-dose) are collected and sent to the appropriate laboratory
- Patients are instructed to return to the site in 4 weeks for Visit 10.

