### **10.3.3 List of criteria for permanent treatment discontinuation**

The patients may withdraw from treatment with the IMP at any time for any reason or this may be the Investigator's decision. Patients should discuss stopping study medication with the site before doing so in order that questions can be addressed, glycemic therapy adjusted, and a follow-up assessment arranged. All efforts should be made to document the reasons for treatment discontinuation and this should be documented in the e-CRF.

The following reasons lead to permanent discontinuation:

- At the patient's own request (ie, withdrawal of consent for treatment)
- If, in the Investigator's opinion, continuation with the administration of the study treatment would be detrimental to the patient's well-being
- Inter-current condition that requires permanent discontinuation of the study treatment as long as the abnormality persists and if the causal relationship of the concerned event and the IMP is possible (according to the Investigator's best medical judgment)
- Pregnancy (in female patients)
- Specific request of the Sponsor

Any abnormal laboratory value will be rechecked immediately for confirmation before making a decision of permanent discontinuation of the IMP for the concerned patient.

For patients who prematurely discontinue the IMP, the assessments planned at EOT visit ([Section 10.1.2.1.2](#)) will be performed at the Premature EOT Visit, scheduled preferably prior to treatment discontinuation or as soon as possible after time of discontinuation the latest at the next on-site visit). Reason for IMP discontinuation will be clearly specified. This Premature EOT assessment may occur at a regularly scheduled visit or at an unscheduled visit.

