## **Appendix B Two-hour standardized mixed meal**

A 2-hour PPG will be obtained after a standardized MM in all patients at Baseline (Day 1, Visit 3) and at Week 26 (Visit 9), or earlier if the patient terminates study participation before Week 26. Any patient who requires the addition of rescue medication should undergo the second standardized MMTT at Visit 9 (Week 26).

The standardized MM must not be done while patients are temporarily off IMP; the Medical Monitor will address any episodes on a case-by-case basis and the standardized MM will be rescheduled when the patient can resume IMP, if applicable.

The first dose of double-blind IMP on Day 1 (Visit 3) will be given AFTER completion of the 2-hour PPG collection. For the Week 26 standardized MM, the patient should take the dose of double-blind IMP immediately after the fasting blood samples are obtained, and approximately 30 minutes **before** ingestion of the standardized MM begins.

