2.1.3 Efficacy endpoints

All efficacy measurements collected during the study will be considered for analyses, including those obtained after IMP discontinuation or introduction of rescue therapy (see [Section 2.5.4](#)).

HbA1c, 2-hour PPG, FPG, urine ACR, UGE, urine GCR, serum creatinine, and eGFR are measured/calculated in a central laboratory (see study flowchart in [\).](#) Body weight, SBP and DBP (see [Section 2.1.4.5](#)) are measured at on-site visits by the investigator. Patients requiring rescue are identified as those with the reason for treatment ticked “rescue therapy” in e-CRF “Medication” page.

Efficacy variables will be summarized in both standard international units and conventional units when applicable.

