2.4.4.1 Analysis of primary efficacy endpoint(s)

The statistical tests will be two-sided tests at a nominal 5% significance level.

Primary analysis

The primary efficacy endpoint of change in HbA1c from baseline to Week 26 will be analyzed by an Analysis of Covariance (ANCOVA) model using HbA1c values measured at baseline and Week 26 (observed or imputed). The missing data at endpoint will be imputed by multiple imputation (MI) methods in 2 parts as detailed below. To be concise, the following texts related to imputation are generalized to accommodate primary as well as continuous secondary efficacy endpoints.

Statistical Analysis Plan

Version: 3

Lexicon Pharmaceuticals Protocol No. EFC14833

Date of Issue: 21-Nov-2019

Covance Study ID: 000000150524

Missing endpoint data at Week 26 (or Week 12 for SBP) visit will be imputed using a model built separately in each treatment group and estimated from the patients in the same treatment group who prematurely discontinue the IMP before the Week 26 (or Week 12 for SBP) visit but have the measurement for the endpoint (ie, retrieved dropouts). The imputation model will include the randomization strata and the corresponding baseline value. In cases of non-convergence during the imputations, the offending stratum will be identified and then will be dropped from the model. Considering that the number of retrieved dropout patients in each treatment group is expected to be small, a simple imputation model based on regression will be used with baseline measurement included as the predictor. This will serve as the primary method of imputation for missing data should sampling criteria be satisfied (see below).

An alternative (back-up) imputation method will be used if the number of patients who prematurely discontinue the IMP before the Week 26 (or Week 12 for SBP) visit but have the measurement for the endpoint is < 5 in any treatment groups (ie, an insufficient number of retrieved dropouts to support the imputation method described above). This criterion will be assessed for each primary or continuous secondary efficacy endpoint.

In the back-up imputation method, missing post-baseline endpoint values at Week 26 (or Week 12 for SBP) will be imputed by the washout Multiple Imputation (MI) method under the missing not at random (MNAR) framework.

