2.4.4.4 Multiplicity issues

To control the family-wise type I error, a fixed-sequence procedure will be applied.

Once the primary variable (change from Baseline to Week 26 in HbA1c) is statistically significant at $\alpha = 0.05$ (2-sided), the following secondary efficacy variables will be tested in the following prioritized order. The testing will stop as soon as an endpoint is found not to be statistically significant at $\alpha=0.05$ (2-sided).

- Comparing sotagliflozin 400 mg versus placebo,
 - Change from Baseline to Week 26 in 2-hour PPG following an MM
 - Change from Baseline to Week 26 in FPG
 - Change from Baseline to Week 26 in body weight
 - Change from Baseline to Week 12 in SBP for patients with baseline SBP ≥ 130 mmHg
 - Change from Baseline to Week 12 in SBP for all patients
 - Proportion of patients with HbA1c $< 7.0\%$ at Week 26
- Comparing sotagliflozin 200 mg versus placebo,
 - Change from Baseline to Week 26 in HbA1c
 - Change from Baseline to Week 26 in 2-hour PPG following an MM
 - Change from Baseline to Week 26 in body weight
 - Change from Baseline to Week 12 in SBP for all patients.

No multiplicity adjustment will be made on efficacy variables other than those mentioned above.

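### 2-hour PPG is not collected after IMP is stopped, so the SAP's retrieved-dropout imputation for this endpoint could draw only on values taken on or near treatment

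*Protocol*

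**What the plan says.** **Collection.** The mixed-meal test is scheduled only at baseline and Week 26. For patients who stop IMP, Protocol 9.1.4.2 asks for a Week 26 visit, "however the MMTT should not be performed at this or any other visit following a Premature EOT visit". The end-of-treatment visit list (Protocol 10.1.2.1.2) marks the test as "not to be performed if patient has discontinued prior to Premature EOT visit". Appendix B adds "The standardized MM must not be done while patients are temporarily off IMP", with the test rescheduled if IMP resumes. Rescued patients who stay on IMP are still tested.

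Two places point the other way. Appendix B has the second test at Week 26, "or earlier if the patient terminates study participation before Week 26". Protocol 10.3.3 says the end-of-treatment assessments "will be performed at the Premature EOT Visit, scheduled preferably prior to treatment discontinuation or as soon as possible after time of discontinuation". Footnote g of the flow chart and section 10.1.2.1.2 both send the reader to section 10.3.4, which does not mention the test.

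**Analysis.** SAP 2.1.3 states: "All efficacy measurements collected during the study will be considered for analyses, including those obtained after IMP discontinuation or introduction of rescue therapy". SAP 2.4.4.1 and 2.4.4.2 impute missing endpoint data first from patients in the same group who stopped IMP early but have the endpoint, provided each group has at least five. Otherwise the washout method is used. On the five-patient rule the SAP says: "This criterion will be assessed for each primary or continuous secondary efficacy endpoint". PPG has no rule of its own. SAP 2.5.4 allows an end-of-treatment value on Day 154 or later to stand for Week 26 when that parameter has no Week 26 measurement.

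**Position.** In SAP 2.4.4.4, "Change from Baseline to Week 26 in 2-hour PPG following an MM" at 400 mg is the first test after the primary endpoint. It appears again in the 200 mg block.

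**The concern.** The retrieved-dropout method imputes patients who stopped and have no value from patients who stopped and were then measured. For HbA1c, FPG and weight the protocol collects such values at Week 26. For PPG it does not, so the outcome after discontinuation is missing by rule rather than by chance. No intermediate PPG exists to inform a model either.

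The SAP's definition of a donor does not require that the value was taken off treatment. A patient tested at a Premature EOT visit on Day 160, still on drug, has discontinued before Week 26 and has a value labelled Week 26, and so qualifies. If five such patients occurred in each group, values taken on or near sotagliflozin would be imputed to sotagliflozin patients who had stopped. This would happen at the test through which every later claim must pass, including HbA1c at 200 mg.

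**Working it through.** **The plan's own figures.** The documents give no sample size for PPG. Their power figures concern HbA1c at 100 per arm, SD 1.2%, two-sided 0.05. With power = Φ(δ / (1.2·√(2/100)) − 1.96):
- δ = 0.6 gives Φ(3.54 − 1.96) = 94.2% (stated 94%).
- δ = 0.5 gives Φ(2.95 − 1.96) = 83.8% (stated 84%).

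Both reproduce, but neither bears on this point.

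**Inputs.**
- Patients per arm, 400 mg comparison: 76/2 + about 100 = 138 (SAP 1.3).
- Patients per arm, 200 mg comparison: about 100.
- Week 26 window: Day 154 onwards (SAP 2.5.4). A stop on Days 154-181 covers 28 of 182 days.
- Donor threshold: five in each group (SAP 2.4.4.1).
- Assumed, because the documents give no rate: a proportion *d* stops IMP, evenly over 182 days, and each is tested at the Premature EOT visit. Range *d* = 8-16%, with 20% as an extreme.

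**Step 1: possible donors.** The window works parameter by parameter, and a returning patient may not have the test at Week 26. A late Premature EOT value is therefore re-labelled whether or not the patient returns. Expected donors per arm = n × d × 28/182:
- d = 8%: 138 × 0.08 × 0.1538 = 1.7
- d = 12%: 138 × 0.12 × 0.1538 = 2.5
- d = 16%: 138 × 0.16 × 0.1538 = 3.4
- d = 20%: 138 × 0.20 × 0.1538 = 4.2

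At 100 per arm, 8-16% gives 1.2-2.5.

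**Step 2: chance that the rule is triggered.** With X ~ Binomial(138, d × 28/182), the probability that both arms of the 400 mg comparison reach five is P(X ≥ 5)²:

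| d | P(X ≥ 5), one arm | both arms |
|---|---|---|
| 8% | 2.9% | 0.1% |
| 12% | 11.3% | 1.3% |
| 16% | 25.4% | 6.4% |
| 20% | 42.0% | 17.6% (about 18%) |

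If the rule must hold in all three groups, the 20% case falls to about 3.5%.

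**Step 3: what changes if it is triggered.** The share still missing is d × 154/182, which is 6.8% at d = 8% and 13.5% at d = 16%. Suppose late on-drug donors carry the full drug effect and washout carries none. The two methods then differ by at most about 7-14% of the on-treatment PPG effect.

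**Step 4: what the restriction costs in data.** If 30-50% of those who stopped attend Week 26 (assumed), the number who could give a measured off-treatment PPG runs from 138 × 0.08 × 0.30 = 3.3 to 138 × 0.16 × 0.50 = 11.0 per arm. Under section 9.1.4.2, none is expected at that visit.

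**The case against.** The strongest reply is that the SAP already copes. The five-donor rule is checked endpoint by endpoint, so PPG goes to the washout method in nearly every plausible case. Washout imputes missing sotagliflozin values from placebo completers, which generally works against the drug. This stands, and it rules out a stronger reading: that PPG has no workable method, or that the first gate carries a demonstrated type I error problem. Nothing in the documents shows either.

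A reader might also infer that every post-baseline PPG is taken on drug and that an off-drug value is impossible. The text does not go that far. Section 9.1.4.2 bars visits following the Premature EOT visit. Section 10.3.3 and Appendix B can be read to allow a test at that visit shortly after the last dose, while section 10.1.2.1.2 excludes it. The defect is that these places disagree.

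Nor does SAP 2.1.3 strictly contradict the protocol. It covers measurements that are collected and does not promise that each test is done off treatment. Its rescue clause does apply to PPG. What remains is a mismatch between the declared analysis and the data collected.

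Finally, the restriction may be deliberate, because the Week 26 test is timed to a dose. Lifting it would also not guarantee five donors. The chance that both 138-patient arms reach five Week 26 returners is about 6% at 8% stopping and 30% returning, and 98% at 16% and 50%. Both points stand, but neither justifies leaving the donor definition open.

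**Conclusion.** The concern holds in a limited form. Under section 9.1.4.2, patients who stopped IMP supply no 2-hour PPG at Week 26. The only values that can satisfy the SAP's retrieved-dropout definition are Premature EOT tests on Day 154 or later, taken on or near treatment: about 1.7-3.4 per arm at 138 per arm. Washout would usually apply. Both arms of the 400 mg comparison reach five donors with probability about 0.1-6% at 8-16% stopping, and about 18% at 20%. The effect on inference is therefore probably modest.

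The point still deserves correction. As written, the rule would impute on-drug values to patients who stopped, at the first gate after the primary endpoint, and nothing in the SAP prevents it. These figures rest on assumed stopping rates, even timing and a test at every Premature EOT visit. Later stopping would raise the donor count, and missed tests would lower it.

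**What to change.** 1. In SAP 2.4.4.2, state that missing 2-hour PPG is imputed by the washout method, and that a Premature EOT mixed-meal test taken on IMP is not a retrieved-dropout donor. Cost: one or two sentences, made before unblinding.
2. Reconcile flow-chart footnote g, Protocol 9.1.4.2, 10.1.2.1.2, 10.3.3, 10.3.4 and Appendix B on whether and when the test is done after IMP is stopped. Cost: wording only.
3. If patients are still in follow-up, align collection with the declared ITT analysis by allowing the meal and 2-hour draw at the Week 26 visit for patients who stopped IMP, subject to the sponsor's clinical judgement. Cost: a protocol change, and a longer visit with one meal and one draw for a few patients. SAP version 3 (21 November 2019) describes the PK sampling as already done, so this may be too late.
4. If it is too late, state in the SAP and the study report that off-treatment PPG was not collected and that the outcome after discontinuation is wholly modelled. Cost: one sentence.
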